5.6 Duration of Therapy

Duration of therapy will depend on individual response, evidence of disease progression and tolerance. In the absence of treatment delays due to adverse events, treatment may continue forever or until one of the following criteria applies:

- Disease progression,
- Intercurrent illness that prevents further administration of treatment,
- Unacceptable adverse event(s),
- Participant demonstrates an inability or unwillingness to comply with the oral medication regimen and/or documentation requirements
- Participant decides to withdraw from treatment but is willing to be followed,
- Participants decides to withdraw consent from the study, or
- General or specific changes in the participant's condition render the participant unacceptable for further treatment in the opinion of the treating investigator.

5.7 Duration of Follow Up

Participants will be followed until death after removal from treatment. This follow-up will be performed by review of the medical record, contact with care providers, and/or telephone contact as needed every 3 months.

5.8 Criteria for Removal from Study

Participants will be removed from treatment when any of the criteria listed in Section 5.6 applies. The reason for discontinuation of treatment and the date the participant was removed must be documented in the study-specific case report form (CRF). Alternative care options will be discussed with the participant.

In the event of unusual or life-threatening complications, participating investigators must immediately notify the Principal Investigator.

6. EXPECTED TOXICITIES AND DOSING DELAYS/DOSE MODIFICATIONS

For patients who do not tolerate the protocol-specified dosing schedule, dose adjustments are permitted in order to allow the patient to continue the study treatment. Details of study treatment schedule adjustments and dose levels are provided in table 6-1:

Table 6-1 Study treatment schedule adjustments and dose levels

Dose level	Dose and schedule
0 (starting dose)	10 mg daily
-1	5 mg daily
-2	5 mg every other day

If a patient has already decreased 2 dose levels, no further dose reduction is permitted. Patients who need an additional dose reduction will be required to discontinue Everolimus.

Dose delays and modifications will be made using the following recommendations. Toxicity assessments will be done using the CTEP Active Version of the NCI Common Terminology Criteria for Adverse Events (CTCAE v4.0) which is identified and located on the CTEP website at: http://ctep.cancer.gov/protocolDevelopment/electronic_applications/ctc.htm.

If possible, symptoms should be managed symptomatically. In the case of toxicity, appropriate medical treatment should be used (including anti-emetics, anti-diarrheals, etc.).

All adverse events experienced by participants will be collected from the time of the first dose of study treatment, through the study and until the final study visit. Participants

continuing to experience toxicity at the off study visit may be contacted for additional assessments until the toxicity has resolved or is deemed irreversible.

6.1 Anticipated Toxicities

A list of the adverse events and potential risks associated with Everolimus appear below and will determine whether dose delays and modifications will be made or whether the event requires expedited reporting **in addition** to routine reporting.

Adverse Reactions Significant:

>10%:

Cardiovascular: Peripheral edema (4% to 45%), hypertension (4% to 30%; hypertensive crisis: 1%)

Central nervous system: Fatigue (7% to 45%), fever (15% to 32%), headache (18% to 30%), seizure (5% to 29%), anxiety/aggression/behavioral disturbance (SEGA: 21%), insomnia (6% to 17%), dizziness (7% to 14%)

Dermatologic: Rash (18% to 59%), acneiform dermatitis (3% to 25%), nail disorders (5% to 22%), acne (3% to 22%), cellulitis (SEGA: 29%), pruritus (13% to 21%), dry skin (9% to 18%), contact dermatitis (14%), excoriation (14%)

Endocrine & metabolic: Hypercholesterolemia (17% to 85%), hyperglycemia (12% to 75%; grades 3/4: <1% to 17%), hypertriglyceridemia ($\leq 73\%$), bicarbonate decreased ($\leq 56\%$), hypophosphatemia (9% to 49%), hypocalcemia (17% to 37%), albumin decreased ($\leq 33\%$), hypoglycemia ($\leq 32\%$), hypokalemia (12% to 29%), hyperlipidemia (renal transplant: 21%), hyperkalemia (renal transplant: 18%), amenorrhea ($\leq 17\%$), hyponatremia ($\leq 16\%$), dyslipidemia (renal transplant: 15%), hypomagnesemia (renal transplant: 14%)

Gastrointestinal: Stomatitis (oncology uses: 44% to 86%; grade 3: 4% to 9%; grade 4: <1%; renal transplant: 8%), diarrhea (14% to 50%; grade 3: $\leq 5\%$; grade 4: <1%), constipation (10% to 38%), abdominal pain (3% to 36%), nausea (8% to 32%; grade 3: $\leq 2\%$; grade 4: <1%), appetite decreased (6% to 30%), anorexia (1% to 30%), vomiting (15% to 29%; grade 3: $\leq 2\%$; grade 4: <1%), weight loss (9% to 28%), taste alteration (1% to 22%), gastroenteritis (1% to 18%), xerostomia (8% to 11%)

Genitourinary: Urinary tract infection (5% to 22%), dysuria (renal transplant: 11%)

Hematologic: Anemia (26% to 92%; grades 3/4: $\leq 15\%$; grade 4: <1%), PTT increased (SEGA: 72%), leukopenia (oncology uses: 26% to 58%; renal transplant 3%), lymphocytopenia (20% to 54%; grades 3/4: $\leq 18\%$), thrombocytopenia (19% to 54%; grade 3: $\leq 3\%$; renal transplant <10%), neutropenia (14% to 46%; grades 3/4: $\leq 9\%$)

13-March-2017

Hepatic: AST increased (23% to 89%; grade 3: \leq 4%; grade 4: $<$ 1%), alkaline phosphatase increased (32% to 74%), ALT increased (18% to 51%; grade 3: \leq 4%; grade 4: $<$ 1%)

Neuromuscular & skeletal: Weakness (13% to 33%), arthralgia (\leq 20%), back pain (11% to 15%), limb pain (8% to 14%)
Otic: Otitis (6% to 36%)

Renal: Creatinine increased (11% to 50%), hematuria (renal transplant: 12%)

Respiratory: Upper respiratory infection (11% to 82%), sinusitis (3% to 39%), cough (7% to 30%), dyspnea (20% to 24%; grade 3: 2% to 6%; grade 4: \leq 1%), epistaxis (\leq 22%), pneumonitis (includes alveolitis, interstitial lung disease, lung infiltrate, pulmonary alveolar hemorrhage, pulmonary toxicity; 1% to 19%; grade 3: 3% to 4%; grade 4: $<$ 1%), nasal congestion (14%), rhinitis (14%), pharyngitis (4% to 11%)

Miscellaneous: Infection (13% to 62%; grade 3: 4% to 7%; grade 4: 1% to 3%)

1% to 10%:

Cardiovascular: Chest pain (5%), tachycardia (3%), heart failure (1%), angina, atrial fibrillation, chest discomfort, deep vein thrombosis, edema (generalized), hypotension, palpitation, syncope

Central nervous system: Depression (5%), migraine (5%), chills (4%), agitation, hallucination, hemiparesis, hypesthesia, malaise, somnolence

Dermatologic: Eczema (10%), alopecia (\leq 10%), palmar-plantar erythrodysesthesia syndrome ([hand-foot syndrome] 5%), papule (5%), erythema 4%, onychoclasia (4%), pityriasis rosea (4%), skin lesions (4%), hirsutism, incision complications, hyperhidrosis, hypertrichosis

Endocrine & metabolic: Menorrhagia (6% to 10%), menstrual irregularities (6% to 10%), diabetes mellitus (exacerbation: 2%; new-onset: $<$ 10%), dysmenorrhea (6%), metrorrhagia (6%), cushingoid syndrome, dehydration, gout, hypercalcemia, hyperparathyroidism, hyperphosphatemia, hyperuricemia, iron deficiency, vitamin B12 deficiency

Gastrointestinal: Gastritis (7%), hemorrhoids (5%), dyspepsia (4%), dysphagia (4%), ageusia (1%), abdominal distention, epigastric discomfort, flatulence, gastroesophageal reflux, gingival hypertrophy, hematemesis, ileus, peritonitis

Genitourinary: Vaginal hemorrhage (8%), bladder spasm, erectile dysfunction, ovarian cysts, pollakiuria, polyuria, pyuria, scrotal edema, urinary retention, urinary urgency

Hematologic: Hemorrhage (3%), leukocytosis, lymphadenopathy, thrombocytopenia

Hepatic: Bilirubin increased (3% to 10%; grades 3/4: ≤1%)

Neuromuscular & skeletal: Muscle spasm (≤10%), tremor (8%), paresthesia (5%), jaw pain (3%), joint swelling, musculoskeletal pain, myalgia, osteonecrosis, osteopenia, osteoporosis, spondylitis

Ocular: Eyelid edema (4%), ocular hyperemia (4%), conjunctivitis (2%), blurred vision, cataract

Renal: Renal failure (3%), BUN increased, hydronephrosis, interstitial nephritis, proteinuria, renal artery thrombosis, renal impairment

Respiratory: Pleural effusion (7%), nasopharyngitis (6%), pneumonia (6%), bronchitis (4%), pharyngolaryngeal pain (4%), rhinorrhea (3%), atelectasis, nasal congestion, pulmonary edema, sinus congestion, wheezing

Miscellaneous: Hypersensitivity (3%; includes anaphylaxis, dyspnea, flushing, chest pain, angioedema), BK virus infection, candidiasis, night sweats

<1% (Limited to important or life-threatening):

Aspergillosis, azoospermia, cardiac arrest, fluid accumulation, graft thrombosis, hepatic cholestasis, hepatitis B reactivation, lymphoma, oligospermia, pancreatitis, pancytopenia, polyoma virus infection (BK virus), progressive multiple leukoencephalopathy (PML), pulmonary embolism, respiratory distress, sepsis, skin cancer, synovitis (severe), testosterone levels decreased, thrombotic microangiopathy/thrombotic thrombocytopenic purpura/hemolytic uremic syndrome (TMA/TTP/HUS), wound healing impaired

6.2 Toxicity Management

Table 6-2 and 6-3 list the dosing guidelines for everolimus-related non-hematologic and hematologic toxicities. Table 6-4 provides guidelines for the management of everolimus-associated pneumonitis.

Table 6-2 Dosing guidelines for Everolimus-related non-hematologic toxicities

Toxicity	Action
Non-Infectious Pneumonitis	Please refer Table 6-4
Reactivation of HBV or HCV flare	Please refer to Section 6.2.1.7.
AST or ALT elevation Grade 1 (> ULN - 3.0 x ULN) Grade 2 (> 3.0 - 5.0 x ULN)	Maintain current dose level
AST or ALT elevation Grade 3 (> 5.0 - 20.0 ULN) *	Interrupt Everolimus administration until resolution to \leq grade 1 (or \leq grade 2 if baseline values were within the range of grade 2). If resolution occurs \leq 7 days, Everolimus should be re-started at the dose level prior to interruption. If resolution takes > 7 days, or if event recurs within 28 days, hold Everolimus until recovery to \leq grade 1 or baseline grade / value and reintroduce Everolimus at one dose level lower, if available. If resolution takes > 28 days, the patient comes off the study.
AST or ALT elevation Grade 4 (> 20 x ULN) *	Interrupt Everolimus administration until resolution to \leq grade 1 (or \leq grade 2 if baseline values were within the range of grade 2). If resolution occurs \leq 7 days, Everolimus should be re-started at one dose level lower. If resolution takes > 7 days, discontinue Everolimus.
Recurrence of grade 4 after dose reduction or toxicity requiring Everolimus interruption for > 28 days	Discontinue Everolimus.
Intolerable grade 2 mucositis, or grade 3 AE, except hyperglycemia or hypertriglyceridemia or hypercholesterolemia	Interrupt Everolimus administration until resolution to \leq grade 1 or baseline grade / value. If resolution occurs within \leq 7 days, Everolimus should be re-started at the dose level prior to interruption. If resolution takes > 7 days, or if event recurs within 28 days, hold Everolimus until recovery to \leq grade 1 or baseline grade / value and reintroduce Everolimus at one dose level lower, if available. Patients will be withdrawn from the study if they fail to recover to \leq grade 1 or baseline grade / value within 28 days.

Toxicity	Action
Any other grade 4 toxicity not listed here, including those involving the cardiac, endocrine, GI, metabolism, musculoskeletal, CNS, renal, respiratory, vascular, and cutaneous systems (CTCAE v4)	Hold Everolimus until recovery to grade \leq 1 or baseline value Reintroduce Everolimus at one dose level lower, if available. If resolution takes $>$ 28 days, the patient comes off the study.
Grade 3 or 4 clinical liver failure (asterixis or encephalopathy/coma)	Discontinue Everolimus
Recurrence of intolerable grade 2 mucositis or grade 3 event after dose reduction	Reduce dose to the next lower dose level, if available. The lowest possible dose level of Everolimus is 2.5 mg daily. Below this level, Everolimus must be discontinued.
Recurrence of grade 4 after dose reduction	Discontinue Everolimus
Any non-hematologic toxicity requiring Everolimus interruption for $>$ 28 days	Discontinue Everolimus, take patient off study
* Should HCV flare be confirmed, the guidelines for flare must take precedence	

Table 6-3 Dosing guidelines for Everolimus-related hematologic toxicities

Toxicity	Action
Grade 2 thrombocytopenia (platelets $<75, \geq 50 \times 10^9/L$)	No action
Grade 3 thrombocytopenia (platelets $<50, \geq 25 \times 10^9/L$)	Interrupt Everolimus until resolution to grade ≤ 1 If resolution occurs ≤ 7 days, reintroduce Everolimus at the dose level prior to interruption. If resolution occurs > 7 days, or event recurs within 28 days, reintroduce Everolimus at one dose level lower, if available. If resolution takes > 28 days, the patient comes off the study.
Grade 4 thrombocytopenia (platelets $< 25 \times 10^9/L$)	Interrupt Everolimus until recovery to grade ≤ 1 . Then reintroduce Everolimus at one dose level lower, if available. If resolution takes > 28 days, the patient comes off the study.
Grade 3 neutropenia or anemia (neutrophil $<1, \geq 0.5 \times 10^9/L$)	Interrupt Everolimus until resolution to grade ≤ 1 or baseline value If AE resolution occurs ≤ 7 days, reintroduce Everolimus at the same dose level. If AE resolution occurs > 7 days, or event recurs within 28 days, reintroduce Everolimus at one dose level lower, if available. If resolution takes > 28 days, the patient comes off the study.
Grade 4 neutropenia or anemia	Interrupt Everolimus until recovery to grade ≤ 1 or baseline value. Reintroduce Everolimus at one dose level lower, if available. * If resolution takes > 28 days, the patient comes off the study.
Febrile neutropenia	Interrupt Everolimus until resolution to grade ≤ 1 (or baseline value) and no fever. Reintroduce Everolimus at one dose level lower, if available. * If resolution takes > 28 days, the patient comes off the study.
Recurrence of grade 3 toxicity after dose reduction	Reduce dose to the next lower dose level, if available.
*Recurrence of grade 4 toxicity (including febrile neutropenia) after dose reduction	Discontinue Everolimus
*Any hematologic toxicity requiring Everolimus interruption for > 28 days	Discontinue Everolimus

Table 6-4 Management of non-infectious pneumonitis

Grade	Required investigations	Management of pneumonitis	Everolimus dose adjustment
Grade 1	CT scans with lung windows.	No specific therapy is required	No dose adjustment required. Initiate appropriate monitoring.
Grade 2	CT scan with lung windows. Consider pulmonary function testing includes: spirometry, DLCO, and room air O ₂ saturation at rest. Consider a bronchoscopy with biopsy and/or BAL. Monitoring at each visit until return to ≤ grade 1. Return to initial monitoring frequency if no recurrence.	Symptomatic only. Consider corticosteroids and/or other supportive therapy if symptoms are troublesome.	Rule out infection and consider interruption of Everolimus until symptoms improve to Grade ≤ 1. Re-initiate Everolimus at one dose level lower. Discontinue Everolimus if failure to recover within ≤ 28 days.
Grade 3	CT scan with lung windows and pulmonary function testing includes: spirometry, DLCO, and room air O ₂ saturation at rest. Monitoring at each visit until return to ≤ grade 1. Return to initial monitoring frequency if no recurrence. Bronchoscopy with biopsy and/or BAL is recommended.	Consider corticosteroids if infective origin is ruled out. Taper as medically indicated.	Rule out infection and interrupt Everolimus until symptoms improve to Grade ≤ 1. Consider re-initiating Everolimus at one dose level lower at investigator discretion. Discontinue Everolimus if failure to recover within ≤ 28 days.
Grade 4	CT scan with lung windows and required pulmonary function testing, if possible, includes: spirometry, DLCO, and room air O ₂ saturation at rest. Monitoring at each visit until return to ≤ grade 1. Return to initial monitoring frequency if no recurrence. Bronchoscopy with biopsy and/or BAL is recommended if possible.	Consider corticosteroids if infective origin is ruled out. Taper as medically indicated.	Rule out infection and discontinue Everolimus.

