6.2.1.7 Management of Hepatitis B and C Reactivation

Patients with a history of hepatitis or significant exposure to hepatitis will be screened at the beginning of the study to assess activity of disease. Those with active hepatitis B or C are excluded from this protocol. Everolimus has been associated with reactivation of both hepatitis B virus (HBV) and hepatitis C virus (HCV). Patients entered on this study who subsequently show evidence of active hepatitis B or C will be withdrawn from the study.

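### For toxicity interruptions longer than 28 days, Tables 6-2 and 6-3 conflict on whether the patient leaves treatment or leaves the study, so survival follow-up could come to depend on toxicity (minor)

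*Combined protocol and SAP*

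**What the plan says.** Section 6.2 handles one trigger, toxicity that keeps everolimus interrupted for more than 28 days, in two ways.

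- **Rows that end study participation.** In Table 6-2, the row for any non-hematologic toxicity says "Discontinue Everolimus, take patient off study". The grade 3 AST/ALT row and the row for other grade 4 toxicities say "If resolution takes > 28 days, the patient comes off the study", and the row for grade 3 events and intolerable grade 2 mucositis withdraws patients who do not recover within 28 days. In Table 6-3, the grade 3 and 4 cytopenia rows and the febrile neutropenia row also take the patient off the study.
- **Rows that only stop the drug.** In Table 6-2, the row "Recurrence of grade 4 after dose reduction or toxicity requiring Everolimus interruption for > 28 days" leads only to discontinuation of everolimus. So does the closing row of Table 6-3, "Any hematologic toxicity requiring Everolimus interruption for > 28 days". Table 6-4 (pneumonitis) likewise only stops the drug after 28 days without recovery.

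Section 6.2.1.7 says that patients who develop active hepatitis B or C "will be withdrawn from the study". Section 5.5 uses similar withdrawal wording for patients who need other anticancer agents.

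Section 5.6 lists unacceptable adverse events among the reasons to stop treatment. Section 5.7 then states: "Participants will be followed until death after removal from treatment". It makes no exception for toxicity. Follow-up is by record review, care-provider contact or telephone every 3 months.

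**The concern.** The same event can send a patient down two paths, depending on which row a site applies. If off study means only off everolimus, the patient enters Section 5.7 follow-up and the date of death is collected. If it means leaving the trial, survival follow-up may end there.

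OS is a secondary endpoint in Section 14.1. It is estimated by Kaplan-Meier, and patients thought to be alive are censored at last follow-up. That estimator assumes that censored patients have the same later risk as those who remain. Toxicity that has not resolved after 28 days is plausibly related to prognosis, so censoring triggered by it could be informative. If those patients do worse, the OS curve would sit too high.

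**Working it through.** The plan states no figure on this point, so there is none to reproduce. The check has two parts.

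**1. Are off treatment and off study the same status?**

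| Place | What it implies |
|---|---|
| Table 6-2, row "Discontinue Everolimus, take patient off study" | Two actions are named; the second is redundant if they mean the same |
| Section 5.6 | Stopping treatment while willing to be followed is listed separately from withdrawing consent from the study |
| Appendix C, Section 5.1 | Monitors review the reason for each status separately |
| Section 5.8 | Headed as removal from study, but the text is about removal from treatment |
| Section 9, study calendar | Everolimus is given until removal from the study, so the terms are merged |
| Section 12.1.2 | One combined form covers both statuses; a separate follow-up/survival form exists |

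The first three places separate the statuses. The next two merge them, and the forms settle nothing. Neither term is defined, so a literal reading and a loose reading are both available to a participating site.

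**2. How large could the effect on OS be if sites read the rows literally?**

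Assumed inputs, none of them in the documents:
- Survival is exponential, with a median of 8 months in patients without prolonged toxicity: h = ln 2 / 8 = 0.0866 per month.
- A fraction f = 0.10 or 0.20 has prolonged toxicity, with hazard r × h from registration and r = 1, 1.5 or 2.
- Those of the fraction still alive at month 3 are censored there.

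Formulas:
- Full follow-up: S(12) = (1 − f)·exp(−12h) + f·exp(−12rh).
- With the censoring: S*(12) = S(3)·exp(−9h), where S(3) = (1 − f)·exp(−3h) + f·exp(−3rh).

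Worked case, f = 0.20 and r = 2:
- S(12) = 0.8 × 0.3536 + 0.2 × 0.1250 = 0.3078.
- S(3) = 0.8 × 0.7711 + 0.2 × 0.5946 = 0.7358.
- S*(12) = 0.7358 × 0.4585 = 0.3374.
- Overstatement: 33.74% − 30.78% = 2.96, or 2.95 points before rounding.

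| f | r | 12-month OS, full | 12-month OS, censored | Difference (points) | Median, full / censored (months) |
|---|---|---|---|---|---|
| 0.10 | 1 | 35.4% | 35.4% | 0 | 8.00 / 8.00 |
| 0.10 | 1.5 | 33.9% | 34.9% | 1.0 | 7.67 / 7.86 |
| 0.10 | 2 | 33.1% | 34.5% | 1.5 | 7.44 / 7.73 |
| 0.20 | 1 | 35.4% | 35.4% | 0 | 8.00 / 8.00 |
| 0.20 | 1.5 | 32.5% | 34.5% | 2.0 | 7.35 / 7.72 |
| 0.20 | 2 | 30.8% | 33.7% | 2.95 | 6.91 / 7.46 |

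The number leaving alive at month 3, per 30 patients, is 30·f·exp(−3rh). This runs from 1.8 (f = 0.10, r = 2) to 4.6 (f = 0.20, r = 1).

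**Sensitivity to the assumptions.** A second set takes 12-month OS as 50% without toxicity withdrawal, censors a fraction d at month 2, and applies hazard ratio r only afterwards. With h = ln 2 / 12, true 12-month OS is exp(−2h)·[(1 − d)·exp(−10h) + d·exp(−10rh)], against a Kaplan-Meier value of 50%. For r from 1 to 3 the overstatement is 0 to 1.7 points at d = 5%, 0 to 3.4 at 10%, and 0 to 6.9 at 20%.

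**Against sampling error.** With 30 patients (the number in Section 14.3) and 12-month OS of 35.4%, the standard error is √(0.354 × 0.646 / 30) = 0.087. The 90% half-width is 1.645 × 0.087 = 0.144, about 14 points.

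**The case against.** The strongest reply is that the plan already answers the question. Unacceptable adverse events are a reason to stop treatment, and Section 5.7 follows everyone removed from treatment until death. Tables 6-2 and 6-3 are dosing guidelines, and both wordings stop the drug. Section 5.8 and the calendar show that study is often written where treatment is meant. This stands to the extent that data loss is nowhere prescribed. It does not remove the conflict between rows, because Section 5.6 and the monitoring plan do separate the two statuses.

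Four stronger readings are tempting, and the documents do not support them.

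- **That survival data are lost.** No passage says that follow-up ends at off study, and filing the combined form does not show it. Loss depends on how sites read the rows.
- **That toxicity follow-up ends.** The introduction to Section 6 allows contact after the off-study visit until toxicity resolves or is deemed irreversible. Section 11.8 follows events up to 30 days after the last intervention to resolution, stability or irreversibility.
- **That progression-free survival (PFS) is biased by this wording.** Section 5.3 lists the 8-weekly scans under the treatment period, Section 5.7 names none, and Sections 10.1.6 and 14.1 censor at the last disease assessment. Progression data after a stop without progression are therefore the same under either wording. The one residual link is a death without documented progression, which counts as a PFS event. It is found or missed along with OS and adds no separate point.
- **That the ambiguity is confined to toxicity.** Section 5.5 uses the same withdrawal wording for patients who need other anticancer agents.

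The size can also be challenged fairly. Section 6.2.1 describes adverse events as mostly mild to moderate and generally reversible, which gives no support for 10-20% with toxicity unresolved beyond 28 days.

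**Conclusion.** The inconsistency is real and can be checked in the current text. Rows with the same 28-day trigger disagree on whether the patient leaves treatment or the study, Section 6.2.1.7 adds to the conflict, and Section 5.7 contains no exception to match. The consequence is conditional: if some sites stop survival follow-up on the strength of the off-study rows, OS censoring would depend on toxicity.

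Under the main assumptions, 12-month OS would be overstated by 0 to about 3 points and the median by 0 to about 0.55 months. The most extreme sensitivity case reaches 6.9 points. The bias is zero if the hazard is the same in those who leave, and it would reverse if they did better. All of these inputs lie outside the documents.

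OS is a descriptive secondary endpoint in a single-arm trial, and the likely bias is small against a 90% half-width of about 14 points. The primary response rule in Section 14.1 counts responses among registered patients, so this wording does not touch it. Severity: minor.

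**What to change.** Reconcile the off-study and withdrawal wording in Tables 6-2 and 6-3, Section 6.2.1.7 and Section 5.5 with Sections 5.6 to 5.8. All dose and treatment-stopping rules stay unchanged; nothing here judges which of them is right.

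1. Define off treatment and off study as separate statuses, and use each term consistently in the tables, the calendar and the heading of Section 5.8.
2. State that patients who stop everolimus for toxicity, including hepatitis reactivation, stay in Section 5.7 survival follow-up and Section 11.8 adverse-event follow-up unless they withdraw consent.
3. In Section 5.5, say which of the two statuses applies to patients who need other anticancer agents.

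The cost is a wording amendment to two tables and a few paragraphs. At most it adds a few of the 3-monthly contacts that Section 5.7 already plans, with no extra scans or visits.
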